7.1 SAFETY ASSESSMENTS

The dose-length product and effective radiation dose will be recorded for all study scans: baseline 18F-fluoride positron emission tomography and computed tomography coronary angiography scan, and the final 2-year computed tomography coronary angiogram.

7.2 STUDY ASSESSMENTS

This is a prospective multi-centre observational cohort study. Subjects will attend for clinical assessments at the screening visit (review of clinical records and confirmation of eligibility), baseline visit (18F-fluoride positron emission tomography, computed tomography calcium scan and CT coronary angiography scan), and at 2 years (repeat computed tomography calcium scan and CT coronary angiogram). Clinical outcome data will be obtained from routinely collected clinical data in the electronic health record and, where appropriate, annual telephone calls to the patients or General Practitioners.

7.2.1 Screening Assessment

Screening visit assessments will include clinical history, review of patient records to confirm study eligibility and record clinical profile, standard clinical biochemical and haematological variables, 12-lead electrocardiogram, the Global Registry of Acute Coronary Events (GRACE) score and the invasive coronary angiogram findings and percutaneous coronary interventional procedures.

7.2.2 Baseline Assessment

Baseline visit assessments will include 18F-fluoride positron emission tomography, computed tomography calcium scan and CT coronary angiography scan. AE/SAE's will also be recorded.

7.2.3 Follow Up Assessments

Participants will be contacted by telephone at 12 months and periodically thereafter until the last recruited patient has completed their 2-year follow-up visit. The purpose of the telephone interview is to review any clinical cardiovascular events that may have occurred in the intervening period. They will attend for a final study visit 2 years after their initial CT-PET scans. At the final study visit, patients will undergo a repeat computed tomography calcium scan and CT coronary angiogram. On-going periodic review of the electronic health records will continue throughout the study and may continue for a period of 5 years after study completion in order to assess long-term outcomes. Additional funding and approval will be sought if this is to continue after study completion.

7.2.4 Positron Emission and Computed Tomography Coronary Angiography

Patients may receive oral and/or intravenous beta-blockade, such as metoprolol 5-100 mg, to slow the heart rate to below 65 beats per minute to maximise image quality and reduce radiation exposure. Glyceryl trinitrate spray or tablet will be administered sublingually (200-400 µg) to induce coronary vasodilatation to enhance image quality of the coronary angiogram.

All patients will undergo dual cardiac and respiratory-gated positron emission and computed tomography imaging of the coronary arteries. Study subjects will be administered a target dose of 250 MBq ¹⁸F-fluoride intravenously and subsequently rested in a quiet environment for 60 min. An attenuation correction computed tomography scan will then be performed, followed by positron emission tomography imaging of the thorax in list-mode for 30 min. Computed tomography coronary calcium scan and angiography will be undertaken in the same visit as the ¹⁸F-fluoride scan and again at 2 years. An electrocardiogram-gated breath-hold computed tomography scan of the coronary arteries will be performed. A bolus of contrast (BMI adjusted) will be injected intravenously after determining the appropriate trigger delay with a test bolus. Because the use of contrast is required for the CT scan study participants may require pre-procedural check of estimated glomerular filtration rate (eGFR) according to local study site imaging protocols. If, however, a participant develops a contraindication to the contrast agent prior to the 2-year computed tomography calcium scan, the computed tomography calcium scan can be performed without contrast.

The positron emission tomography scans will be reconstructed in multiple phases of the cardiac cycle, with the diastolic phase (50-75%) used for analysis. Additional reconstructions will be undertaken as necessary. Positron emission tomography scans will correct for cardiac motion correction using electrocardiogram-gated images.

Further technical details of the specific CT-PET scanning procedures and how inter-site imaging standardisation will be achieved will be described in a separate scanning document.

7.3 SUB-STUDY ASSESSMENTS

There will be three main sub-studies in relation to coronary ¹⁸F-fluoride uptake that will assess (i) short-term reproducibility, (ii) time course, and (iii) *in vivo* plaque characterisation. These will be performed only at the lead centre in Edinburgh and are described in more detail in separate protocols. Any participant will only be involved in one sub-study that requires a repeat ¹⁸F-fluoride positron emission tomography and computed tomography coronary angiogram in addition to the main PRE¹⁸FFIR study protocol.

7.3.1 Short-term Reproducibility (PRE¹⁸FFIR-REPRO)

Following the baseline assessments, a repeat 18F-fluoride positron emission tomography and computed tomography coronary angiogram will be performed within 21 days of the initial scan. This will allow the assessment of scan-rescan reproducibility. This will be performed in 20 patients.

7.3.2 Time Course (PRE¹⁸FFIR-TIME)

Following the baseline assessments, a repeat 18F-fluoride positron emission tomography and computed tomography coronary angiogram will be performed within, 12±2, 26±2 and 52±2 weeks of the initial scan. This will allow a description of the natural history of 18F-fluoride uptake and positivity. This will be performed in three cohorts of 20 patients each. Any single patient will only undergo a maximum of two 18F-fluoride positron emission tomography and three computed tomography coronary angiography scans.

7.3.3 *In Vivo* Plaque Characterisation (PRE¹⁸FFIR-IMAGE)

In 80 patients, intravascular ultrasound, near infra-red spectroscopy and optical coherence tomography will be performed on the culprit and control non-culprit lesions at the time of invasive coronary angiography. This will permit detailed characterisation of plaque composition and structure with which to compare the 18F-fluoride positron emission tomography and computed tomography coronary angiography scans.

8 DATA COLLECTION

All trial data will be recorded onto paper case record forms (CRF) by a member of the research team and then entered into an electronic database designed and developed by the Edinburgh Clinical Trials Unit.

9 DATA MANAGEMENT

9.1.1 Personal Data

The following personal data will be collected as part of the research:

- Participant's name
- Address and contact details
- Date of birth
- GP contact details
- Community Health Index (CHI) number or National Health Service (NHS) number.

9.1.2 Data Information Flow

The participant's name, address and contact details will be used by the research teams at the sites to contact their patients to arrange study visits. The GP contact details will be used by the research staff at sites to send a letter to the participant's GP advising them their patient is taking part in the trial. The participant's date of birth and CHI/NHS number will be collected and used to perform record linkage with national health registries to assess the long-term outcomes of heart artery inflammation. All personal data will be stored securely for a minimum of 5 years after the study has finished.

9.1.3 Transfer of Data

Data collected or generated by the study may be transferred to external individuals or organisations outside of the Sponsoring organisation(s). It may be provided to researchers running other research studies outwith NHS Lothian/University of Edinburgh. Following publication of the primary paper, a de-identified individual participant data set will be submitted to a data archive for sharing purposes. Participant information will only be used by organisations and researchers to conduct research in accordance with the [UK Policy Framework for Health and Social Care Research](#). Where this information includes identifiable information, it will be held securely with strict arrangements about who can access the information.

In order to perform data linkage participant's personal details including their CHI number or NHS number will be transferred to national health registries, central NHS bodies and NHS boards.

9.1.4 Data Controller

A data controller is an organisation that determines the purposes for which, and the manner in which, any personal data are processed.

The University of Edinburgh and NHS Lothian are joint data controllers along with any other entities involved in delivering the study that may be a data controller in accordance with applicable laws (e.g. the site)

9.1.5 Data Breaches

Any data breaches will be reported to the University of Edinburgh and NHS Lothian Data Protection Officers who will onward report to the relevant authority according to the appropriate timelines if required.

10 STATISTICS AND DATA ANALYSIS

10.1 SAMPLE SIZE CALCULATION

Based on the assumption that one third of patients will have multiple 18Ffluoride positive plaques, and that the proportion of patients who have died or had a recurrent myocardial infarction by one year will be 30% in patients with multiple 18F-fluoride positive plaques, and 20% in other patients, we need 692 (231+461) subjects (power=80%, p= 2 sided 0.05). This proportion of events is

conservative, as we observed 20% deaths or recurrent myocardial infarctions at 1-year in consecutive unselected patients hospitalised with myocardial infarction [Mills et al, 2011; Mills et al, 2012]. In our preliminary data [Joshi et al, 2014], 25-45% of patients had untreated 18F-fluoride positive plaques. This calculation is from a continuity corrected chi-squared test. As the analysis will be time-to-event, we would expect to need 10% fewer patients, and therefore this calculation allows for 10% missing data.

10.2 PROPOSED ANALYSES

10.2.1 Description of Analysis Sets

The primary analyses will be based on all patients who have undergone the initial CT-PET scan.

10.2.2 Methods of Statistical Analysis

The primary analysis will be performed by calculating Kaplan-Meier estimates of the ‘survival’ curves for the time to first event (cardiac death, recurrent myocardial infarction, or unscheduled coronary revascularisation) during follow up, and comparing these estimates for patients with and without coronary microcalcification activity using a log-rank test. The results will be expressed as the estimated hazard ratio with the corresponding 95% confidence interval and p value. Patients who die during follow-up whose deaths are not classified as cardiac deaths will be censored in the above analysis at the time of death.

Since 18F-fluoride uptake is a continuous measure, a potentially more sensitive analysis will explore the relationship between uptake and the risk of suffering an event (cardiac death, recurrent myocardial infarction, or unscheduled coronary revascularisation). This will be performed using the Cox proportional hazards regression model, with (transformed) 18F-fluoride uptake as the only covariate. A range of potential transformations of the 18F-fluoride update will be explored, including fractional polynomials, to find an optimal fit to the data. Once an appropriate transformation for the 18F-fluoride uptake has been identified (as above), the Global Registry of Acute Coronary Events (GRACE) score will be added into the Cox proportional hazards model, to assess the incremental prognostic value of 18F-fluoride over and above conventional clinical risk markers.

11 ADVERSE EVENTS

The Investigator is responsible for the detection and documentation of events meeting the criteria and definitions detailed below.

Full details of contraindications and side effects that have been reported following administration of the IMP are described in the study Investigator’s Brochure.

Participants will be instructed to contact their Investigator at any time after consenting to join the trial if any symptoms develop. All adverse events (AE)

as defined in section 11.2 that occur after joining the trial must be reported in detail in the Case Report Form (CRF) or AE form. In the case of an AE, the Investigator should initiate the appropriate treatment according to their medical judgment.

11.1 DEFINITIONS

An **adverse event** (AE) is any untoward medical occurrence in a clinical trial participant which does not necessarily have a causal relationship with an investigational medicinal product (IMP).

An **adverse reaction** (AR) is any untoward and unintended response to an IMP which is related to any dose administered to that participant.

A **serious adverse event** (SAE), **serious adverse reaction** (SAR). Any AE or AR that at any dose:

- results in death of the clinical trial participant
- is life threatening*
- requires in-patient hospitalisation** or prolongation of existing hospitalisation
- results in persistent or significant disability or incapacity
- consists of a congenital anomaly or birth defect
- results in any other significant medical event not meeting the criteria above

*Life-threatening in the definition of an SAE or SAR refers to an event where the participant was at risk of death at the time of the event. It does not refer to an event which hypothetically might have caused death if it were more severe.

**Any hospitalisation that was planned prior to randomisation will not meet SAE criteria. Any hospitalisation that is planned post randomisation will meet the SAE criteria.

A suspected unexpected serious adverse reaction (SUSAR) is any AR that is classified as serious and is suspected to be caused by the IMP, that it is not consistent with the information about the IMP in the Investigator's Brochure.

11.2 IDENTIFYING AEs AND SAEs

There will be a 48 hour time window to collect and record all AEs and SAEs which occur as a result of the 18F-fluoride intravenous injection and which occur during the 18F-fluoride PET and CT angiogram scanning visits including administration of the beta blockade, glyceryl trinitrate, contrast agent and radiation exposure. Patients attending the scanning visits will be asked to contact the research team if they experience any untoward effects within 48 hours of the scans. Only AEs/SAEs experienced during the scan and selfreported within 48 hours of the PET and /or CT scan will be recorded in the AE log and SAE form, respectively. Any AEs or SAEs out with the above

definitions will not be recorded during the study although data on hospitalisations and deaths will be collected for long-term outcomes.

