2.2.3 Safety Endpoints

- Dose-length product and effective radiation dose associated with PET and CT scans.
- Adverse events experienced during the scan or self-reported within 48 hours of PET and CT scans.

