11.5 REPORTING OF SAEs/SARs/SUSARs

Once the Investigator becomes aware that an SAE has occurred in a study participant, the information will be reported to the ACCORD Research Governance & QA Office **immediately or within 24 hours**. If the Investigator does not have all information regarding an SAE, they should not wait for this additional information before notifying ACCORD. The SAE report form can be updated when the additional information is received.

The SAE report will provide an assessment of causality and expectedness at the time of the initial report to ACCORD according to Sections 11.4.2, Assessment of Causality and 11.4.3, Assessment of Expectedness. The SAE form will be transmitted by fax to ACCORD on **[name]** or may be transmitted by hand to the office or submitted via email to [contact]. Only forms in a pdf format will be accepted by ACCORD via email.

Where missing information has not been sent to ACCORD after an initial report, ACCORD will contact the investigator and request the missing information. All reports faxed to ACCORD and any follow up information will be retained by the Investigator in the Investigator Site File (ISF).

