5.5 Safety analyses

5.5.1 To determine the radiation exposure and effective dose associated with ¹⁸F-fluoride positron emission tomography and computed tomography coronary angiography

The following will be presented for the scanned population. Details of radiation exposure for patients in the safety population who are not in the scanned population will be put in a footnote.

Table: mean, standard deviation, median, lower and upper quartile, minimum, and maximum of injected ¹⁸F-fluoride activity (MBq) and effective radiation dose (mSv) from administration of radioactive tracer at baseline visit. The effective radiation dose (mSv) will be calculated from the administered dose using the conversion factor of 0.024 mSv/MBq. Mean, standard deviation, median, lower and upper quartile, minimum, and maximum of dose-length product (Gy·cm) and effective radiation dose (mSv) from computed tomography component of the scans at baseline visit. The effective radiation dose (mSv) will be calculated from the dose-length product using the conversion factor of 0.014 mSv/Gy·cm. Mean standard deviation, median, lower and upper quartile, minimum, and maximum of total effective radiation dose (mSv) at baseline visit.

The following will be presented for the participants who had a CT scan at 2 years.

Table: mean, standard deviation, median, lower and upper quartile, minimum, and maximum of dose-length product (mGy·cm) and effective radiation dose (mSv) from the scans at 2-year visit. The effective radiation dose (mSv) will be calculated from the dose-length product using the conversion factor of 0.014 mSv/Gy·cm.

These tabulations will not be split by CMA status.

5.5.2. To identify adverse events associated with ¹⁸F-fluoride positron emission tomography and computed tomography angiography

The following will be presented for the safety population.

Table: summary of adverse events within 48 hours of baseline visit showing both numbers and percentages of patients with events, and number of events. Also present these numbers split by whether events are serious or non-serious, and within seriousness by (i) causality (unrelated or possibly related for IMP and NIMP) and MedDRA preferred term (or an alternative classification), and (ii) MedDRA system organ class and MedDRA preferred term (or an alternative classification). No formal statistical analysis will be performed.

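### Protocol 11.2 limits AE/SAE recording by when and by whom an event is reported rather than by its onset, and conflicts with its own opening sentence, 2.2.3, 11.5, 13.3 and SAP 5.5.2

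*Combined protocol and SAP*

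**What the plan says.** Protocol 11.2 makes four statements about what is captured.

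- It opens with a general promise that carries no self-report condition: "There will be a 48 hour time window to collect and record all AEs and SAEs which occur as a result" of the tracer injection and at the scanning visits.
- It describes how events after the visit come to light: "Patients attending the scanning visits will be asked to contact the research team if they experience any untoward effects within 48 hours of the scans".
- It then restricts what is entered on the AE log and SAE form: "Only AEs/SAEs experienced during the scan and selfreported within 48 hours of the PET and /or CT scan will be recorded".
- It closes by saying that AEs or SAEs outside its "definitions will not be recorded during the study although data on hospitalisations and deaths will be collected for long-term outcomes".

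The safety endpoint in 2.2.3 is worded differently: "Adverse events experienced during the scan or self-reported within 48 hours of PET and CT scans".

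Elsewhere, the introduction to section 11 states: "Participants will be instructed to contact their Investigator at any time after consenting to join the trial if any symptoms develop". The same paragraph ties the duty to report AEs to the definition in 11.2. Section 11.5 starts the SAE route on awareness: "Once the Investigator becomes aware that an SAE has occurred in a study participant", a report goes to the sponsor's office at once or within 24 hours. Section 13.3 explains that there is no data monitoring committee and that all SAEs go to the sponsor and the steering committee. SAP 5.5.2 plans a "summary of adverse events within 48 hours of baseline visit", and listings of events within 48 hours of the baseline and 2-year visits.

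**The concern.** A safety window is normally defined by when an event starts. The restricting sentence in 11.2 uses instead whether the participant reported it, and whether that report came within 48 hours. Someone who is incapacitated, admitted elsewhere or dead cannot make that report, so the condition bears hardest on the most serious events.

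Adverse events of the scans are a stated safety objective (2.1.3) and endpoint (2.2.3), and the tracer has no marketing authorisation (6.1.3). If a site follows the restricting sentence, an SAE with onset inside the window may get no SAE form. Under 11.5 that report carries the causality and expectedness assessments, and it starts the route to expedited SUSAR reporting in 11.6. If another site follows 11.5, it will report the same kind of event. The 48-hour table in the SAP would look like a complete count by onset, while the data behind it had been filtered in a way that may differ between sites.

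**Working it through.** The plan gives no figure to reproduce and no arithmetic applies. The check is to take each type of event and ask what each wording does with it.

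| Event | 11.2 as written (*and*) | 2.2.3 wording (*or*) | Window defined by onset |
|---|---|---|---|
| A. Starts in the scan, self-reported within 48 h | recorded | recorded | recorded |
| B. Starts in the scan, seen by staff, not self-reported | not recorded | recorded | recorded |
| C. Starts after the scan within 48 h, self-reported within 48 h | not recorded | recorded | recorded |
| D. Starts after the scan within 48 h, self-reported later (say onset at hour 10, report at hour 60) | not recorded | not recorded | recorded |
| E. Starts after the scan within 48 h, known only from hospital records (say an admission or death at hour 20) | not recorded | not recorded | recorded |
| F. Starts after 48 h | not recorded | not recorded | not recorded |

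Rows B and C depend on *and* versus *or*. Rows D and E do not: they are lost under both wordings, so changing the conjunction alone does not solve the problem. Row F is outside the window on any reading.

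Next, do other sections bring rows D and E back?

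1. **Opening sentence of 11.2.** It covers all AEs and SAEs in its scope without a self-report condition, so it would admit row E. Whether its 48 hours times the onset or the collection is not stated, so row D is unclear.
2. **Introduction to section 11.** Participants may make contact at any time, but the AEs to be reported are those defined in 11.2, which leads back to the restriction.
3. **Section 11.3.** The investigator reviews hospital notes once an AE or SAE occurs, and onset date is among the items collected. This helps to describe an event, but does not say that one outside 11.2 is to be recorded.
4. **Sections 11.5 and 13.3.** Awareness triggers the SAE report, and all SAEs reach the sponsor and steering committee. Read on their own, these capture rows D and E when the event is serious and the site knows of it. That is directly opposed to the closing statement of 11.2.
5. **Outcome data.** Section 11.2 keeps hospitalisations and deaths for long-term outcomes, and all-cause death is a secondary endpoint (2.2.2). A death in row E is therefore detected, but 11.2 gives it no route to an SAE form.
6. **SAP 5.5.2.** The table and listings use 48 hours from the visit and do not mention self-report. They can place any recorded event by its onset date, but cannot restore one that was never recorded.

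Ascertainment after the visit is also passive. Table 1 schedules no contact at 48 hours for the main study, and the first planned telephone review is at 1 year.

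**The case against.** The strongest reply is that this is loose drafting with adequate safeguards. Section 11.2 should be read as a whole: it begins with all events in a 48-hour window, and its request to participants is naturally read as timing the effects rather than the telephone call. Investigators must report SAEs once aware, all SAEs go to the steering committee, and deaths and admissions are collected anyway. The AE tables are descriptive, have no formal testing and are not split by CMA status, and a limited window is a stated choice for a single injection of an established tracer.

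Much of this stands, and it rules out several stronger readings that a reader might infer:

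- *That such reactions are excluded from safety recording altogether.* Sections 11.5 and 13.3 say the opposite. The defect is a contradiction.
- *That only reactions starting in the scanner count.* This rests on the literal *and*. Since 2.2.3 has *or*, and since asking participants to report later effects would otherwise be pointless, *and* is probably a slip.
- *That the steering committee sees only self-reported SAEs.* Section 13.3 sends it all of them.
- *That reports of reactions to the unlicensed tracer are equally at risk at both visits.* In the main study the 2-year visit is CT without tracer, so that argument applies to the baseline visit only.
- *That omitting events after 48 hours is the fault.* That limit is a deliberate choice and is not challenged here.

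What the reply does not remove is the restricting sentence. It says *only*, it is followed by an explicit instruction not to record the rest, and section 11 makes 11.2 the reference for AE reporting. A site that follows it is complying with the protocol.

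**Conclusion.** The point holds as an internal inconsistency with a practical consequence. In its operative sentence, 11.2 selects events by the time and source of the report. Under either conjunction this leaves out events with onset after the scan but within 48 hours that are reported late or learned of only from records, including deaths. That conflicts with the opening sentence of 11.2 (which sets no self-report condition), with 11.5, 13.3 and SAP 5.5.2.

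At risk are the SAE classification, causality assessment and expedited reporting of such events, and the completeness of the 48-hour AE table. Detection of deaths and hospitalisations as outcomes is not at risk, and the primary analysis is unaffected. The filter can only remove events, so any bias in the AE count is downward. Its size cannot be estimated: the documents give neither an AE rate nor any figure for reporting delay. The conclusion assumes only that some sites would apply the restricting sentence as written.

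**What to change.** Reword 11.2 and 2.2.3 so that they state one rule: record every AE and SAE with onset from the first study administration at a scanning visit (tracer, contrast, beta-blocker or glyceryl trinitrate, as applicable) to 48 hours after the PET and/or CT scan, whatever the source of the information and whenever it becomes known. Delete the self-report condition and the *and*/*or* difference goes with it. State in 11.5 that SAEs meeting this definition are reported on awareness, so that 11.5, 13.3 and SAP 5.5.2 all refer to the same set of events.

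Add a check of the hospitalisation and death data against each participant's scan dates, and enter any event with onset in the window on the SAE form for reporting under 11.5.

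The cost is a protocol amendment of a few sentences and one date-matching query. Onset date, hospitalisations and deaths are already collected. The downside is a few extra SAE forms, some of them for coincidental admissions after the infarction.
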